
Justification

We wish to demonstrate that the use of with autologous MSCs is effective as a treatment option for knee OA grades, II and III. In a large number of cases it is possible to improve the pain, function and quality of life of patients without the side effects of conventional treatments. In other cases, avoid progression to more severe stages that require joint replacement surgery. This research aims at contributing with a low-cost regenerative technique in order to change the course of the disease and significantly reduce public and private sector expenses generated by conservative and surgical OA treatments.

Main goals

- a. The aim of the present study will be to compare three types of intra-articular injections of MSC populations obtained from two clinically relevant sources: injections containing BM-MSC or AD-MSC or a combination of both of them BM-MSC and AD-MSC, in a randomized non blind clinical trial.
- b. To assess the efficacy and safety of treatment with containing BM-MSC or AD-MSC or a combination of both of them BM-MSC and AD-MSC, in relation to pain, function and quality of life in patients with knee OA.

Hypothesis Testing

H1: The combined use of BM-MSC and AD-MSC is superior for pain management in knee OA, than the use of BMSC or AD-MSC alone.

H0: The combined use of MSC from bone marrow and adipose tissue is not superior to the use of MSC derived solely from bone marrow or solely from adipose tissue in the treatment of pain and function in patients with knee OA.

MATERIALS AND METHODS

1. Study design

The present study will be conducted from June 2020 to December 2021 at the Omnihospital, an affiliated center to the Universidad Católica de Santiago de Guayaquil Ecuador, and the support of the Instituto de Investigación e Innovación de Salud Integral, Medical Faculty of the same University and Maastricht University, The Netherlands. This will be a phase III trial, triple arm randomized open label dose to be conducted as a single intra-articular injection of MSC in 3 groups of patients with the diagnosis of knee OA grade II and III (Ahlbäck classification),²² one receiving BM-MSC other receiving AD-MSC and the other BM-MSC + AD-MSC.

2. Study population

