A total of 54 patients with the diagnosis of knee OA grade II and III will be recruited to receive a single intra-articular injection of MSC: Group 1 (n 18 patients) will receive BM-MSC and Group 2 (n 18 patients) will receive AD-MSC, and Group 3 (n 18 patients) will receive BM-MSC + AD-MSC.

a. Inclusion criteria:

- i. Patients aged 18 to 70 years, with grade II and III knee OA, according to the Ahlbäck classification will be included. Identified by two different observers.
- ii. Minimal VAS pain score of 4.
- iii. Chronic knee pain of mechanical origin.
- iv. All patients who sign a specially prepared informed consent for this clinical trial.

b. Exclusion criteria:

- i. Varus or valgus knee mal alignment superior to 10°.
- ii. OA grade IV according Ahlbäck classification.
- iii. Bone marrow cancer like lymphoma.
- iv. Severe anemia.
- v. Active infections.
- vi. Pregnant patients.
- vii. Immune diseases such as Rheumatoid arthritis, gout or pseudogout arthritis, psoriasis.
- viii. Bone diseases such as Kahler and Paget.
- ix. Corticoesteroid and hyaluronic injections within the last 3 months.
- x. Knee surgery in the last 6 months.

3. Ethical considerations

- a. All patients will be informed of the study aims and have the choice to complete an informed consent.
- b. All patients will be informed about alternative treatments.
- c. This study will be approved by the Ethical Committee of Catholic University of Santiago de Guayaquil (UCSG).

4. Evaluations

a. Pre-Operative:

- i. Complete clinical and orthopedic evaluation.
- ii. Laboratory diagnostic tests (biometrics, coagulation parameters glycemia, and liver, pancreatic, renal and lipid profile).
- iii. Radiological exams: Knee X Rays with weight bearing.
- iv. Magnetic resonance of the knee with cartilage measurement. T2 Map. MRI T2 mapping of the cartilage is a non-invasive functional imaging technique delivering cartography of the T2 relaxation time of the cartilage without any contrast injection. It is sensitive to tissue anisotropy, and provides compositional information on the cartilage collagen network, water content and proteoglycans concentration.

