This study applies descriptive statistics for determining the frequency and proportions for demographic variables (age, gender, education, and ethnicity) and clinical states (severity of knee osteoarthritis, time with disease, comorbidities). Likewise, for calculating the mean and standard deviation of age, WOMAC scores (and each element of the scale) and VAS.

We utilize the two-way mixed ANOVA to compare the differences of means between treatment groups for each dependent variable (WOMAC scores, VAS, and radiological changes). With respect to the WOMAC scores, not only we will analyze the scores in general, but also each score value of the three different components separately (pain, stiffness, function). The tests will determine if there is an interaction between the dependent variable and the factors (independent variables). The factors will be the type of treatment (between subjects) and time (within subjects). For the type of treatment, it

is categorized into: BMSCS only, AD-MSc only, and BM-MSc and AD-MSc combined.

As for the time factor, this will differ according to the dependent variable held for analysis. For example, the analysis of WOMAC and EAV scores will be evaluated in 6 different periods of time. The patients will be asked to respond to our questionnaires three weeks before the intervention and 1, 3, 6, 9, and 12 months after intervention (surgery). With respect to radiological changes, the T2 mapping MRI will be performed twice before the procedure and again six months later.

To guarantee the reliability of the analysis, we will test the atypical values by utilizing box diagrams and the normality with the method of Shapiro-Wilk. Furthermore, the homogeneity of variations will be evaluated with inferential statistic Levene tests, while the homogeneity of covariances with multivariate statistical Box's M test. Consequently, to comply with the hypothesis sphericity, a Mauchly's test will be conducted. In the case of a violation of an assumption, different tests will be utilized.

Finally, in the case of a treatment complication, there will be mixed lineal models generalized for determining the probability of each intervention. The complications considered in this investigation are pain and hematomas in the surgical place where stem cells were extracted, knee pain, and synovial effusion.

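### The planned three-arm interaction test has no direction and no contrast is specified, so it cannot support H1; baseline-adjusted contrasts of the combination against each single source would

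*Combined protocol and SAP*

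**What the plan says.** Statistical Analysis names the model: "We utilize the two-way mixed ANOVA to compare the differences of means between treatment groups for each dependent variable". It then gives the terms: "The factors will be the type of treatment (between subjects) and time (within subjects"). On what is tested it says "The tests will determine if there is an interaction between the dependent variable and the factors (independent variables"). For the questionnaires, "the analysis of WOMAC and EAV scores will be evaluated in 6 different periods of time", and these are "three weeks before the intervention and 1, 3, 6, 9, and 12 months after intervention". The pre-treatment score is thus an outcome at one level of time, not a covariate. No planned contrast, pairwise comparison, post hoc procedure or multiplicity rule appears. If an assumption fails, unspecified other tests will be used.

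Under Hypothesis Testing, H1 states that the combination "is superior for pain management in knee OA, than the use of BMSC or AD-MSC alone". H0 states that it "is not superior to the use of MSC derived solely from bone marrow or solely from adipose tissue", and extends this to function as well as pain.

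The flow chart puts baseline VAS, WOMAC and MRI T2 at Visit 2 (week 2), randomisation at Visit 4 (week 4) and the procedure at Visit 5 (week 6). The sample size is computed for the interaction: f = 0.25, alpha 0.05, power 0.95, three groups, three repetitions, correlation 0.5, giving 54.

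**The concern.** An interaction F test over three arms asks whether the arms' time profiles differ in any way. H1 asks whether one particular arm is better than the others. The first can be true when the second is false, or when its opposite is true. If follow-up comparisons are intended, they are unwritten. They would then be chosen after open-label data have been seen, across VAS, WOMAC total, three WOMAC subscales and MRI.

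The baseline score is also used inefficiently wherever an arm is compared with its own baseline. It is collected before randomisation, so it is a valid covariate at no extra cost. This stays true if it is taken three weeks before a week-6 procedure, because that is week 3.

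**Working it through.** **Inputs.** From Statistical Analysis: N = 54 (18 per arm), correlation rho = 0.5, sphericity, f = 0.25, six questionnaire time points. Assumed: complete data, equal SDs, constant correlation, and an effect present at every post-treatment visit. Effects are in SD units; 0.7 SD is an illustrative value.

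**1. The plan's own figure.** lambda = f² × N × m / (1 − rho) = 0.0625 × 54 × 3 / 0.5 = 20.25, with df 4 and 102. Power is 0.958. N = 51 gives 0.946, so 54 is correct.

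**2. Size of effect.** If one arm differs by d at every post-treatment visit, f = d × √((2/9) × v). Here v = 2/9 with three time levels and 5/36 with six. So f = 0.25 at three levels is d = 1.125 SD. The same d is f = 0.198 at six levels.

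**3. The six-level interaction.** lambda = 18 × (2/3) × (5/6) × d² / (1 − rho) = 20d², with df 10 and 255.
- d = 1.125: lambda 25.3, power 0.95.
- d = 0.7: lambda 9.8, power 0.51.

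The term 2/3 comes from squared deviations between arms. It is the same whichever arm is the odd one out, and in either direction.

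**4. Does rejection track H1?** Simulation, 20,000 trials per row. The last column requires both baseline-adjusted month-12 contrasts to favour the combination, each at two-sided 0.05.

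| Truth (1.125 SD) | Interaction rejects | Both contrasts |
|---|---|---|
| Combination better than both | 0.95 | 0.94 |
| Combination worse than both | 0.95 | 0.000 |
| Combination equals AD-MSC, both worse than BM-MSC | 0.95 | 0.000 |
| Combination equals BM-MSC, AD-MSC worse | 0.95 | 0.026 |

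**5. Power for H1 on VAS or WOMAC.** The baseline-adjusted variance is 1 − rho² = 0.75 for one visit, and (1 + 4rho)/5 − rho² = 0.35 for the mean of five visits. For a sustained 0.7 SD advantage over both sources:
- both contrasts, mean of five visits: 0.88
- both contrasts, month 12 only: 0.50
- planned interaction: 0.51
- planned treatment main effect: lambda = 12 × (5d/6)² / ((1 + 5rho)/6) = 7.0, df 2 and 51, power 0.63; also without direction

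**6. MRI T2, two scans.** The planned interaction is then exactly a change-score test: lambda = 12d² / (2(1 − rho)) = 12d², df 2 and 51. ANCOVA divides lambda by 0.75 × 50/49 = 0.765 (the factor 50/49 is the cost of estimating the slope), df 2 and 50. With two levels, f = 0.25 is d = 1.06.

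**MRI T2, three scans (two before the procedure).** Planned: lambda = 18 × (2/3) × (2/3) × d² / 0.5 = 16d², df 4 and 102. ANCOVA on the mean of the two baselines has residual variance 1 − 0.25/0.75 = 0.667.

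| Scans | d | Planned | ANCOVA |
|---|---|---|---|
| Two | 1.06 | 0.90 | 0.96 |
| Two | 0.7 | 0.55 | 0.67 |
| Three | 1.06 | 0.93 | 0.98 |
| Three | 0.7 | 0.57 | 0.73 |

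**7. Effect of the VAS entry rule.** Entry requires "Minimal VAS pain score of 4", which may narrow the baseline spread. With slope fixed at 0.5 and baseline SD equal to s times its unrestricted value, the variance of an adjusted contrast relative to a change score is 0.75 / (0.75 + 0.25s²). This is 0.75 at s = 1, 0.82 at s = 0.8 and 0.92 at s = 0.5.

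**The case against.** The plan does not claim that a significant interaction proves H1. It also reports means and SDs by arm, so the direction would be visible. That is fair: the defect is that no test of H1 is pre-specified, not that a false inference is written down.

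A reader might infer from the variance ratio of 0.75 to 0.77 that the planned VAS and WOMAC analysis wastes about a quarter of its information. The documents do not support this. The ratio is against a single-visit change-score contrast, which the plan does not contain for these outcomes. A month-12 contrast pair has about the same power as the planned interaction (0.50 against 0.51); its advantage is that it answers H1. Only MRI T2 is a like-for-like comparison, and H1 concerns pain.

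H1's wording also leaves open whether the combination must beat both sources or either. The last row of the first table counts against H1 only under the both reading. If either suffices, with each contrast at 0.025, the month-12 rule succeeds there with probability about 0.93. The second and third rows are H1-false on any reading, so the main conclusion does not depend on this choice.

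The mean of five visits gains only if the effect is sustained. A 0.7 SD effect confined to month 12 would shrink to 0.7/5 = 0.14 SD on the mean.

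Finally, an unstructured mixed model is heavy for 54 patients: 15 covariance and 20 mean parameters, and an overall F with simulated size of 0.07 to 0.08. That is a reason for a simpler model, not for omitting the contrasts.

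**Conclusion.** The point holds and is worth correcting before analysis. The planned interaction rejects with probability about 0.95 under H1, under its opposite, and when the combination merely equals one source. It cannot by itself support the trial's stated hypothesis. The equality across patterns follows from the formula. The value 0.95 rests on a sustained 1.125 SD difference, correlation 0.5 and complete data.

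Two stronger readings should be resisted. The analysis is not biased, since randomisation protects the comparison with or without adjustment. The sample size is not wrong for the test it was computed for. The precision gain from adjustment is firm for MRI T2 under either reading of the scan schedule. For VAS and WOMAC a power gain over the planned interaction is shown only for the mean of the post-treatment visits with a sustained effect. The gain depends on the correlation, and for VAS it is smaller if the entry threshold narrows the baseline spread.

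**What to change.** Amend the Statistical Analysis section as follows. No new patients, visits or measurements are needed.

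- Name one pain outcome for H1. Test it by baseline-adjusted contrasts of the combination against BM-MSC and against AD-MSC. Treat the interaction as supportive.
- Pre-specify the summary: the mean of the post-treatment visits, or one named visit. The plan names none.
- State whether both contrasts must succeed (each at 0.05) or either suffices (Holm). Requiring both is a stricter rule than the omnibus test.
- Reconcile H0, which covers pain and function, with H1, which covers pain only.
- Fit a simple ANCOVA, or a mixed model of the post-treatment scores with baseline as covariate and a pre-stated simpler covariance in case the unstructured one is too heavy.
- Analyse MRI T2 by ANCOVA of the 6-month value on arm and baseline. If two pre-procedure scans are intended, use their mean as the covariate.
- Reconcile three schedule points first. Statistical Analysis can be read as two MRI scans before the procedure, whereas Evaluations and the flow chart show one. The month-1 VAS and WOMAC visit appears in Evaluations, Follow Up and Statistical Analysis but not in the flow chart. Baseline is three weeks before the intervention in Statistical Analysis, but week 2 with the procedure in week 6 in the flow chart. If the month-1 visit is dropped, the mean is over four visits and its adjusted variance becomes (1 + 3 × 0.5)/4 − 0.25 = 0.375 instead of 0.35.

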- i. AD-MSC will be joined with BM-MSC in a same syringe for application of the percutaneous injection (AD MSC + BM MSC group) into the affected knee.

7. FOLLOW UP.

All patients will be evaluated measuring scores of the WOMAC (Western Ontario and McMaster Universities Osteoarthritis Index)²³ and the VAS (Visual Analogue Scale), before treatment and then at 1, 3, 6, 9 and 12 months.

STUDY FLOW CHART
MSC IN OA

Patient: _____

STUDY FLOW CHART	VISIT 1	VISIT 2	VISIT 3	VISIT 4	VISIT 5	VISIT 6	VISIT 7	VISIT 8	VISIT 9	VISIT 10
Protocol Concept Sheet	Week 1	Week 2	Week 3	Week 4	Week 6	Month 3	Month 6	Month 9	Month 12	Month 15
Diagnosis	X	X								
Orthopaedic exam	X									
X RAYS		X								
MRI T2 map		X								
Laboratory		X								
Inclusion/Exclusion		X								
Informed Consent		X								
Pre Op Evaluations		X								
VAS		X								
WOMAC		X								
Preparation	X		X							
Randomization				X						
Procedures					X					
BM MSC					X					
AD MSC					X					
Flow Citometry Order					X					
Post Op Evaluations					X					
Sticks removed					X					
VAS						X	X	X	X	
WOMAC						X	X	X	X	
MRI T2 map							X			
Adverse Event Evaluation					X	X	X	X	X	
Results										X

MD. Signature

Date.

[figure not shown]
Figure 2. Clinical Trial MSC/OA Protocol Sheet.

Statistical Analysis.

The sample size is determined using the tool of G*Power VERSION 3.0.10. The parameters are applied for the selected F test, two-way mixed ANOVA (repeated measures, with immediate interaction). Given that none of these approaches have been previously compared, either separately or combined, the calculation was conducted considering a medium effect size ($f=0.25$). We established an error probability α of 0.05 and power of 0.95. We calculated the application of 3 repeated measures, even though 6 measures will be conducted for some variables (i.e., the VAS or WOMAC questionnaire).

Based on this criteria, the sample size would be 54, meaning that each group will consist of 18 individuals. The information previously mentioned is represented in detail in the following table and illustrated in a graph below it.

F tests - ANOVA: Repeated measures, within-between interaction		
Analysis:	A priori: Compute required sample size	
Input:	Effect size f	= 0.25
	α err prob	= 0.05
	Power (1- β err prob)	= 0.95
	Number of groups	= 3
	Repetitions	= 3
	Corr among rep measures	= 0.5
	Nonsphericity correction ϵ	= 1
Output:	Noncentrality parameter λ	= 20.250000

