Data will be analyzed using SPSS software version 24.0. for every test, a *p-value* lower than 0.05 will be considered as the statistical significance level.

SAFETY

Absence of immunological reaction and disease transmission due to the fact that MSCs belong to the same patient. Wakitani²⁷ from the University of Osaka Japan demonstrated in an 11-year follow-up study that MSC did not induce tumor growth or infection in any patient treated for cartilage lesions.

Chris and colleagues²⁸ reported no adverse events after using intra-articular injection of 1.0×10^8 AD MSCs in patients with knee OA, and showing improvement of joint function.

Peeters et al²⁹. evaluated 8 studies that involved 844 MSC-treated patients with intra-articular injected culture expansion. They concluded that there are no opposing arguments for the intra-articular application of MSC.

Systematic reviews have all been in favor of the safety in intra-articular - injections of MSCs. However, great caution is warranted with culturing and expansion of MSCs³⁰.

DISCUSSION

The function of MSCs has been explored under the influence of bioactive carriers such as platelet-rich plasma (PRP). Platelets contain greater than 1500 protein based factors

with bioactive ability³¹. This broad spectrum of compounds includes growth factors, peptide hormones, chemokines, fibrin and also proteins with anti-bacterial and fungicidal properties.

Growth factors released by platelets may potentially play a positive role in the up regulation of MSCs. TGFβ1 is seen to reduce collagen type I gene expression and up regulate expression of collagen type II and aggrecan genes³². Further, TGFβ1 works in association with basic Fibroblast Growth Factor (FGF2) to assist in the migration of stromal cells to a site of injury^{30,33}.

The combination of PRP with MSCs in intra-articular injections has shown increased collagen type II expression and reduced chondrocyte apoptosis³⁴.

Most recently, Phase I and II trials using expanded adipose derived MSCs in the treatment of OA have shown MRI evidence of cartilage regrowth³¹. Following a single intra-articular injection of 100 million MSCs, radiological (MRI) follow-up at 6 months showed increased cartilage volume³⁰.

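### The two-way mixed ANOVA discards, outcome by outcome, every patient with one missed assessment, and the 54 recruited leave no allowance for loss; a mixed model on all available scores avoids this

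*Combined protocol and SAP*

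**What the plan says.** The Statistical Analysis section sets one method for VAS, WOMAC (total and three components) and radiological change: "We utilize the two-way mixed ANOVA to compare the differences of means between treatment groups for each dependent variable". Treatment is the between-subjects factor and time the within-subjects factor, and the tests are meant to show whether the two interact. The number of time points depends on the outcome: "the analysis of WOMAC and EAV scores will be evaluated in 6 different periods of time", namely before treatment and at 1, 3, 6, 9 and 12 months, while T2-map MRI is analysed before the procedure and at six months. On software: "Data will be analyzed using SPSS software version 24.0".

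The sample size comes from G*Power for the within-between interaction, with f = 0.25, three groups, correlation 0.5 and nonsphericity correction 1. The plan adds: "We established an error probability α of 0.05 and power of 0.95" and "We calculated the application of 3 repeated measures, even though 6 measures will be conducted for some variables". The result is that "the sample size would be 54, meaning that each group will consist of 18 individuals". The Study population section recruits the same 54.

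The plan gives no dropout rate, missing-data rule, imputation method, analysis population or provision for patients who withdraw. Two passages might seem to help but do not. The clause on switching to other tests applies only when a model assumption fails. Generalised mixed models are planned only for complications.

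**The concern.** A classical mixed ANOVA, with the Mauchly and Box's M checks that the plan lists, needs a value at every level of the time factor for each patient. The plan never says that it will analyse complete cases only; the method it names imposes that. A patient who attends five of six VAS assessments contributes nothing to the VAS analysis.

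Two things are at stake. The first is efficiency: valid scores are thrown away, and there is no reserve of patients behind the stated power of 0.95. The second is validity. The trial is open-label, follow-up lasts 12 months, and NSAIDs are restricted for 12 months after the procedure. Patients with persistent pain therefore have a plausible reason to leave, and they know their arm. If leaving differs by arm, those who complete are no longer the groups that were randomised.

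**Working it through.** **1. Reproduce the plan's figure.** Inputs from the G*Power table: f = 0.25, k = 3 groups, m = 3 measures, ρ = 0.5, ε = 1, α = 0.05.

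- λ = f²·N·m·ε/(1 − ρ) = 0.0625 × 54 × 3 / 0.5 = 20.25, as printed in the plan.
- df1 = (k − 1)(m − 1)ε = 4; df2 = (N − k)(m − 1)ε = 51 × 2 = 102.
- Power from the noncentral F distribution = 0.958.

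The smallest total reaching 0.95 is 52, or 54 in three equal groups. The figure is correct and contains no allowance for loss.

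**2. Power by number of complete patients.** Same formula. The six-measure columns use the number of VAS and WOMAC time points in the planned analysis; ε = 0.6 is an assumption.

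| Complete patients | m = 3, ε = 1 (plan) | m = 6, ε = 1 | m = 6, ε = 0.6 |
|---|---|---|---|
| 54 | 0.958 | 0.998 | 0.971 |
| 51 | 0.946 | 0.996 | 0.961 |
| 48 | 0.930 | 0.994 | 0.948 |
| 45 | 0.911 | 0.990 | 0.931 |
| 42 | 0.887 | 0.984 | 0.909 |

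For example, at N = 42 and m = 6, λ = 0.0625 × 42 × 6 / 0.5 = 31.5 with 10 and 195 degrees of freedom. With ε = 0.6, λ = 18.9 with 6 and 117.

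**3. How many patients might be excluded.** The documents give no missed-visit rate, so a range is assumed. If each of the five follow-up assessments is missed independently with probability p, the share with an incomplete set is 1 − (1 − p)⁵:

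- p = 0.03: 14%, about 8 of 54
- p = 0.05: 23%, about 12 of 54
- p = 0.10: 41%, about 22 of 54

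If misses cluster in the same patients, fewer are excluded.

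**4. Bias, by simulation.** All settings are assumptions: 18 per arm, VAS SD 2, correlation 0.5, true 12-month difference −1.0. Patients whose last VAS was 5 or more leave at 20% per visit in a single-source arm and 5% in the combination arm. About 27–29% against 4–8% end up incomplete, depending on the assumed mean trajectories.

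- 12-month arm difference among completers: −0.74 to −0.76. A likelihood model on all scores gives −1.00.
- Arm difference averaged over follow-up: truth −0.78, completers −0.49, likelihood model −0.79.
- Arm difference in change from baseline among completers: −1.00 to −1.02, and −0.98 under an autoregressive correlation.
- Interaction test among completers: rejects 5.1% of the time with no true effect. With the true −1.0, power falls from 0.25 to 0.20.

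The −1.00 for the likelihood model comes from generalised least squares with the true covariance. A covariance matrix estimated from 54 patients would be less precise.

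**The case against.** The strongest reply concerns the test that the plan actually powers. That is the treatment-by-time interaction, with baseline as one of its time levels, so it works on within-patient change. In the simulations change from baseline is nearly unbiased among completers and the type I error is held. A reader might infer that completer analysis shrinks the effect that H1 looks for. The documents do not support that: they name no raw 12-month arm contrast as the hypothesis test, and for the interaction the loss seen is one of precision. This part of the objection stands, within the covariance and dropout patterns tried.

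A reader might also infer that the trial is underpowered. That does not follow either. The fall to 0.946 at 51 uses three measures, while the outcomes most exposed to missed visits have six. With six measures and ε = 1, 36 complete patients still give 0.960. The margin is smaller if sphericity fails.

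Three further points stand. Exclusion is per outcome: a patient missing the month-9 VAS can stay in the MRI analysis, and the complication models do not depend on a complete VAS set. The missed-visit and leaving rates are assumed. And nothing in the documents says that patients will regard a single-source arm as inferior, since all three arms receive active cells.

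None of this answers the core point. The named method discards partial data, and nothing in the plan offsets that.

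**Conclusion.** The point holds as one of efficiency and of unspecified handling of incomplete data; it should be corrected, but it does not invalidate the design. What is certain, as soon as any assessment is missed, is that valid scores are discarded and precision is lost for that outcome. On the plan's three-measure inputs, the stated 0.95 survives the loss of at most two patients (52 is the minimum). On six measures there is real margin, with 0.984 at 42 under sphericity and 0.909 under an assumed ε of 0.6.

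Bias depends on assumptions that the documents neither state nor exclude. If leaving depends on pain and differs by arm, post-baseline arm means and the treatment main effect are distorted among completers, by about a quarter of a true 12-month difference of −1.0 in the scenario simulated. The planned interaction is nearly unbiased in the scenarios tested; other covariance or dropout patterns could change that.

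**What to change.** - Replace the two-way mixed ANOVA with a linear mixed model for repeated measures (SPSS MIXED): arm, visit as a categorical factor, and arm-by-visit. Fit it to all available scores of all randomised patients in their assigned arm.
- State the covariance structure, a simpler fallback if the unstructured one does not converge (with six visits it has 6 × 7 / 2 = 21 parameters for 54 patients), and a small-sample degrees-of-freedom method.
- State that scores already collected from patients who stop attending are kept, and that these patients are asked for VAS and WOMAC at the remaining scheduled times.
- Restate the 0.95 power as assuming no loss, and show it for both three and six measures.

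The cost is SAP wording: the planned software includes the procedure, and no patients or visits are added. The small downsides are more model specification and a power statement that becomes conditional. The change retains partial data but does not build in an allowance for loss; restating the power makes that explicit.
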